9.4.10. New RSV LRTI episode rule

A new episode of an event is a single case of RSV RTI, RSV LRTI, severe RSV LRTI, or hospitalization meeting the respective case definitions and severity scale with an interval of at least 7 symptom free days since the last episode that was diagnosed. (Note: persistent runny nose is an exception to the 7 symptom free days rule. A child may have persistent runny nose but still present with a new episode of RSV LRTI). If symptoms worsen within 7 days, the subject comes for a worsening visit.

Figure 5 Derivation of 2 RSV LRTI events date and duration with a symptom free period of at least 7 days

9.4.11. Symptoms

9.4.11.1. Increased respiratory rate

The subject will be considered to have increased respiratory rate if one of the following statements is reached:

- Respiratory rate (field [sctRESPIRATORYRATE_RTI])
- > 60/minute for subjects <2 months of age (fields [sctDEMOGRAPHY.itmDOB_RAW] and [rscRESPIRATORYRATE_RTI.VSORRES_RESP])
- > 50/minute for subjects 2-11 months of age(fields [sctDEMOGRAPHY.itmDOB_RAW] and [rscRESPIRATORYRATE_RTI.VSORRES_RESP])
- > 40/minute for subjects 12-24 months of age(fields [sctDEMOGRAPHY.itmDOB_RAW] and [rscRESPIRATORYRATE_RTI.VSORRES_RESP])

Please note that respiratory rate is measured during the general and obstetric physical exam.

9.5. Statistical Methods

9.5.1. Computation of incidence rates

For each endpoint, the incidence rate (IR, number of episodes/endpoints per 100 person-years) will be calculated by dividing the number of subjects reporting the first episode over the follow-up period by the total person-year. A 95% CI will be computed using an exact method for a Poisson variable as described below.

The person-time at risk for an event of interest (RSV-LRTI or RSV hospitalization) will be calculated as the time between the date of birth and the end of the at-risk period or the earliest of the followings:

- Date of first diagnosis of event of interest (e.g. first episode of RSV-LRTI);
- Date when child reaches 1 year (or 6 months if analysis is done during the interim analysis);
- Date of death;
- Date of last follow-up in study.

Please note that in a case where a subject comes to an assessment visits, has LRTI symptoms, is not confirmed for RSV infection via a nasal swab (because either no nasal swab was taken or the lab yielded invalid results), then we will consider the subject as not have a laboratory-confirmed event. The Subject will therefore be censored at the event ($n=0$, T =from start of the follow-up period at risk up to event).

9.5.2. Exact confidence intervals (CIs)

The exact confidence interval within a group for an incidence rate (per 100 person-years):

To estimate the confidence limit of the incidence rate, the exact Poisson confidence limit will be used [[Clopper](#), 1934]:

If n is the number of subjects presenting a given characteristic among these Ny subjects per year, the true incidence rate can be estimated by $(n/Ny)*100$. Its exact $(1-\alpha)\%$ confidence interval is obtained from:

$$CINV(\alpha/2, 2*n)/2/Ny*100 \text{ as the lower boundary}$$

and

$$CINV((1-\alpha)/2, 2*(n+1))/2/Ny*100 \text{ as the upper boundary.}$$

where $CINV(\text{probability, degrees of freedom})$ returns the inverse of the chi-squared probability distribution and α is the type I error rate.

9.5.3. Computation of proportion affected

Proportion affected will be computed as the number of subject who had at least one episode in the age interval divided by the total number of subjects at start of considered age strata. A 95% CI will be computed using an exact method for a Poisson variable.

9.5.4. Computation of incidence proportion

Incidence proportion will be computed as the number of subjects who had at least one episode in the age interval (monthly) divided by the number of subject at risk of event at the beginning of the age interval. A subject that has an event will no longer consider of at risk, i.e. subjects with event in 0 – 1 month are excluded from denominator for future monthly incidence calculation. A 95% CI will be computed using an exact method.

9.5.5. Cox models

All multivariable modelling will be done in a stepwise manner using backward elimination and statistical significance.

9.5.5.1. Univariate Models

Please see section 5.4.4.2. Univariate modelling will be done to first determine which risk factors are associated with which event of interest.

For each potential risk factor:

- Frequency tables will be generated as appropriate, for categorical variables.
- Mean, median, standard error, minimum, maximum and number of missing values will be provided as appropriate, for continuous data.

For pairwise distributions:

- Cross-tabulations (i.e. two-way frequency tables) will be generated as appropriate, for categorical-categorical pairs;
- Mean, median, standard error, minimum, maximum and number of missing values by category will be provided as appropriate, for continuous-categorical pairs;

9.5.5.2. Multivariable Models

Covariate selection will be done using statistical significance: the final multivariable regression models will include all potential risk factors with a simple regression model with p-value < 0.10. The number of covariates included in the models will depend on the number of events (at least 10 events per covariate). The models will be performed only if the number of events is sufficient (at least 10 events per covariate). In addition, depending on the data and the validity of the model assumptions, other models could be explored or the models could be simplified.

The results from the multivariable regression models will include hazard ratios (Cox regression models) and odds ratios (logistic and longitudinal logistic regression models) and their 95% CI.

9.5.5.3. Multiple Logistic Regression models

Multiple logistic regression models will be used to test the association between events of interest and risk factors. PROC LOGISTIC or PROC GENMOD can be used. What is tested will depend on how many people are observed with these outcome and risk factors and if they are associated in the univariate analysis.

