Repeat incidence analyses described in section 5.3.6 with alternative LRTIs/Severe LRTIs case definitions.

5.4.4. To determine risk factors for pregnancy related and neonatal events of interest.**5.4.4.1. Analysis of risk factors for pregnancy related and neonatal events of interest as described in the protocol.**

- Both pregnancy related events of interest and neonatal events of interest will be described according to variables collected in the mother's clinical examination and obstetric risk factors. Frequency tables will be generated for categorical variables.
- Furthermore, multiple variable analyses (such as multiple logistic regression for binary outcomes and multiple Poisson/negative binomial and/or other appropriate models for count outcomes) will be conducted to adjust for covariates of interest, provided there are sufficient numbers of events of interest.

5.4.4.2. Additional considerations:

This analysis will be performed on the maternal and infant PPSs depending on whether the risk factors are for pregnancy-related events of interest or for neonatal events of interest.

There are currently 14 potential pregnancy related events of interest and 9 potential risk factors. Likewise, there are 12 potential neonatal events of interest and 13 potential risk factors. (These do not include GAIA subcategories).

Univariate modelling will be done to first determine which risk factors are associated with which event of interest.

For each potential risk factor,

- Frequency tables will be generated as appropriate, for categorical variables.
- Mean, median, standard error, minimum, maximum and number of missing values will be provided as appropriate, for continuous data.

For pairwise distributions

- Cross-tabulations (i.e. two-way frequency tables) will be generated as appropriate, for categorical-categorical pairs;
- Mean, median, standard error, minimum, maximum and number of missing values by category will be provided as appropriate, for continuous-categorical pairs;

Covariates with univariate p-value less than 0.1 will be included in the multivariable model. The number of covariates included in the model will depend on the number of events (at least 10 events per covariates).

Multiple logistic regression, multiple Poisson regression/negative binomial modelling will be used when appropriate only on risk factors and events of interest that were associated in the univariate analysis and provided there are sufficient numbers of events of interest.

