8. CHANGES FROM PLANNED ANALYSES

Only the first episode within a given age interval is considered for the computation of incidence. The incidence of event is computed using three different calculation methods: incidence rate, proportion affected, and incidence proportion. See section 5.3.6 for details of calculation.

In analysing incidence of RSV LRTI and RSV Hospitalization, only the first episode of each will be considered.

A correction from the analysis planned in protocol in section 5.3.5.1 is that we will be reporting on all cause LRTIs and RSV associated LRTIs.

Analyses will be stratified by country and by age strata (mother or infant depending on the analysis).

In instances where there are low frequencies (either in events of interest or case definitions) results may be presented by region in addition to by country (see Section 9.3 for subgroups).

The cohort have been adjusted in Amendment 4 of the protocol. See section 4 in the SAP for details. Analyses will be conducted on PPS cohorts. If there is a difference of 5% or more between the number of participants in the enrolled set and the PPS, analyses will also be performed on enrolled sets.

India has been removed from the study and Bangladesh and Panama have been added.

Alternative LRTI/Severe LRTI case definitions have been added to the study and subsequent analyses.

The interim analyses is no longer planned and may only occurred if deemed necessary.

Considering the COVID19 pandemic, Primary analysis (all subjects have completed all study visit in Epoch 002) will be conducted using as clean as possible data based on the status of the data monitoring defined by the pre-defined proportion of Maternal Subjects Assigned to the SDV/SDR Scheme defined in the monitoring plan.

In addition to the pre-defined analysis, sensitivity analysis will be also conducted, as appropriate, based on the % of maternal and infant subjects reaching the threshold of 70% SDV/SDR scheme as defined in the monitoring plan.”

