9.1.3. Risk factors for pregnancy-related and neonatal events of interest

Table 9 Risk factors for pregnancy-related events of interest

Risk Factor	Categories
Prenatal smoking exposure during this pregnancy	Yes/No
Alcohol consumption during this pregnancy	Yes/No
BMI pre-pregnancy (kg/cm ²)	Continuous
Age of mother at delivery in current pregnancy(years)	18-34 ≥35
Subject currently lives in a country or region with Zika transmission	Yes/No
Subject has travelled to a country or region with Zika transmission since the beginning of their pregnancy	Yes/No
Subject travelled to country or region with Zika virus transmission	Yes/No
Predominant geographic ancestry	African Heritage/African American American Indian or Alaskan Native Asian-Central/South Asian Heritage Asian-East Asian Heritage Asian-Japanese Heritage Asian-South East Asian Heritage Native Hawaiian or Other Pacific Islander White Middle-eastern /North African Heritage White-Caucasian/ European Heritage Latino/Mestizo Other
Caesarean section in previous pregnancy	Yes/No
Highest education level of mother	High education Yes: Bachelor's degree or higher No: Less than bachelor's degree

Table 10 Risk factors for neonatal events of interest

Risk Factor	Categories
Prenatal smoking exposure during this pregnancy	Yes/No
Age of mother at delivery in current pregnancy (years)	18-34 ≥35
Alcohol consumption during this pregnancy	Yes/No
BMI pre-pregnancy (kg/cm ²)	Continuous
Gestational diabetes mellitus in current pregnancy	Yes/No
Gestational hypertension in current pregnancy	Yes/No
Fetal growth restriction	Y/N
Antenatal bleeding	Y/N
Dysfunctional labor	Y/N
Gender of new-born	Male/Female
Subject lives in or travelled to country or region with Zika virus infection during pregnancy	Yes/No
Predominant geographic ancestry	African Heritage/African American American Indian or Alaskan Native Asian-Central/South Asian Heritage Asian-East Asian Heritage Asian-Japanese Heritage Asian-South East Asian Heritage Native Hawaiian or Other Pacific Islander White Middle-eastern /North African Heritage White-Caucasian/ European Heritage Latino/Mestizo Other
Apgar at 5 minutes of age	0-3 inclusive 4-6 inclusive 7 or greater

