9.5.5.2. Multivariable Models

Covariate selection will be done using statistical significance: the final multivariable regression models will include all potential risk factors with a simple regression model with p-value < 0.10. The number of covariates included in the models will depend on the number of events (at least 10 events per covariate). The models will be performed only if the number of events is sufficient (at least 10 events per covariate). In addition, depending on the data and the validity of the model assumptions, other models could be explored or the models could be simplified.

The results from the multivariable regression models will include hazard ratios (Cox regression models) and odds ratios (logistic and longitudinal logistic regression models) and their 95% CI.

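### The pooled risk-factor models do not account for country, so differences between the ten countries can be reported as effects of person-level factors

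*SAP*

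**What the plan says.** The references are to the current text (SAP Amendment 2). The key sentence of 9.5.5.3 is the same in all three versions bound in the file.

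- **Model.** 9.5.5.3: "Multiple logistic regression models will be used to test the association between events of interest and risk factors". Section 5.4.4.2 (risk factors) adds Poisson or negative binomial models where appropriate.
- **Population.** 5.4.4.2 uses the maternal and infant per-protocol sets. The opening of 5.4 has tertiary analyses done overall, with region or another grouping as a possibility.
- **Candidates.** 5.4.4.2: "There are currently 14 potential pregnancy related events of interest and 9 potential risk factors" and "Likewise, there are 12 potential neonatal events of interest and 13 potential risk factors". Table 9 in fact lists ten factors; Table 10 lists 13. They include "Prenatal smoking exposure during this pregnancy", alcohol, pre-pregnancy BMI, maternal age, "Predominant geographic ancestry" and Zika residence or travel. Maternal education is in Table 9 only. Neither table lists country, region or site.
- **Selection.** 5.4.4.2: "Covariates with univariate p-value less than 0.1 will be included in the multivariable model". 9.5.5.2: "The number of covariates included in the models will depend on the number of events (at least 10 events per covariate").
- **Country in general.** Section 8: "Analyses will be stratified by country and by age strata (mother or infant depending on the analysis"). The sentence after it says that results may be presented by region as well as by country when frequencies are low.

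**The concern.** The SAP treats country as important elsewhere: event frequencies, incidence and co-infections are all reported by country. The risk-factor models are where it drops out. If both an exposure and an event, or its diagnosis, are more common in some countries than in others, the pooled odds ratio combines the within-country association with the between-country one. The univariate screen is also run without country, so selection is exposed as well as estimation. The tertiary objective is to determine risk factors, and odds ratios with 95% CIs will be reported. A factor with no effect in any country could be named as a risk factor, and a real one could be masked.

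**Working it through.** The SAP gives no power, effect size or country-specific rates for these models, so it has no figure to reproduce. What follows shows the mechanism and its possible size.

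**Inputs from the SAP:** about 2300 women (2.1); ten countries (9.3, although 2.1 says nine); 200 to 300 women per country (2.1), hence 2300/10 = 230 on average; screen at p<0.1; at least 10 events per covariate.

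**Assumed, not in the SAP:** event rates and exposure prevalences by country.

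**1. Closed form, no true effect.** Half the countries have 5% events and 10% exposed; half have 15% and 40%. Within each country the odds ratio is 1.
- Risk in the exposed: (0.10×0.05 + 0.40×0.15)/(0.10 + 0.40) = 0.065/0.50 = 13%.
- Risk in the unexposed: (0.90×0.05 + 0.60×0.15)/(0.90 + 0.60) = 0.135/1.50 = 9%.
- Pooled odds ratio: (0.13/0.87)/(0.09/0.91) = 1.51.

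Milder contrasts give less. Exposure 5% v 15% with events 5% v 7.5% gives 1.12. Exposure 5% v 40% with events 5% v 15% gives 1.66.

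**2. Crude simulation.** 10×230 women, no within-country effect, event rate centred at 8%, exposure centred at 20%, country deviations drawn independently on the logit scale, 8000 runs per row. The crude 2×2 odds ratio with a Wald interval is set against the Mantel-Haenszel odds ratio stratified by country.

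| Country SD on logit (events / exposure) | Crude 95% CI excludes 1 | Stratified by country |
|---|---|---|
| 0.3 / 0.5 | about 5% | about 5% |
| 0.5 / 1.0 | about 12% | about 5% |
| 0.7 / 1.0 | about 17–18% | about 5% |
| 1.0 / 1.0 | about 28–29% | about 5% |
| 1.0 / 1.5 | about 39% | about 5% |

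Across these rows the p<0.1 screen passes the null factor in about 10–11% (smallest spread) to 47% (largest) of runs.

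**3. Does ancestry repair it?** In a separate logistic simulation (400 replicates, true odds ratio 1), each country was assigned to one of four ancestry groups.
- Exposure and event rate varying together *within* ancestry groups: OR 1.33 unadjusted (p<0.05 in 33%), 1.27 with ancestry (26%), 0.98 with country (4.5%).
- Event rates differing only *between* ancestry groups: OR 1.06 unadjusted, 1.01 with ancestry.

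In the setting of step 2 at moderate spread (rows 2 and 3), stratifying by ancestry lowers the false-positive rate to 6–7% if half the country variance lies between ancestry groups, and to 10–15% if none does.

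**4. Could Section 8 mean separate models per country?** At 8% events, 230×0.08 ≈ 18 events, which allows one covariate. Ten covariates need 100 events: 100/230 = 43% of a country's women, against 100/2300 = 4.3% pooled.

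**The case against.** The strongest reply is that Section 8 already calls for stratification by country, and that a stratified model is not the same as ten separate models. That is right, so step 4 alone does not dispose of the sentence. But the sentence pairs country with age strata and is followed by one on presenting results, so it reads as a rule for tables. Section 5.4.4.2 gives no by-country instruction, unlike 5.2, most of 5.3 and 5.4.1. A programmer following the model sections would fit no country term. A reader might infer that the SAP is silent on country; it is not. The two places need reconciling.

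Second, the lists are of potential factors at present, and 9.5.5.2 lets other models be explored. This leaves room for a country term but commits to none.

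Third, ancestry and Zika residence carry geographic information, and ancestry would often pass the screen when event rates differ: in about 77–97% of runs at moderate to large spread, if ancestry follows four country groups. This stands as a reduction. It is not a cure, because Latino/Mestizo can span five countries.

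Fourth, the analysis is tertiary and Section 6 advises caution. That limits the stakes, but the stated reason for caution is multiplicity, which is a different problem from confounding. No primary or secondary result is affected.

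**Conclusion.** The concern holds as a risk created by the plan as written: country differences *can* be reported as effects of smoking, alcohol, BMI, maternal age and, for pregnancy events only, education. A reader might go further and infer that the reported odds ratios will be wrong, or that the percentages above are the error rates of the planned multivariable models. The documents do not support either. The SAP gives no country spreads, and at the smallest assumed spread the false-positive rate is the nominal 5%. The range of about 5% to 39% comes from a crude table with no other covariates, and an ancestry term would lower it by an amount that depends on how country differences align with ancestry. Nor does the concern reach education in the neonatal models, because Table 10 does not list it. The change is worth making because country is known for every subject and the bias is avoidable at little cost.

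**What to change.** In 5.4.4.2 and 9.5.5.2–9.5.5.3, with a matching line in 9.5.6:

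1. Account for country in both the univariate screen and the multivariable models for person-level factors. Do not screen it by p-value or count it against the 10-events limit.
2. For binary outcomes, use logistic regression conditional on country (a STRATA statement in PROC LOGISTIC). For Poisson or negative binomial models, include a country effect such as a random intercept. State that the estimates are within-country.
3. Report the Zika residence and travel factors separately, without conditioning on country, and label them as between-country associations, since they are largely geographic.
4. Amend Section 8 to say whether its country sentence governs tables, models or both.

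**Cost.** SAP wording and small program changes; no new data. Entering country as nine indicator variables would instead use 9×10 = 90 events (3.9% of 2300) under the 10-events rule, which conditioning avoids. Countries with no events add nothing to the conditional models, and ancestry and Zika residence are estimated within country only where they vary.

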9.5.6. Multiple Poisson/negative binomial models

PROC GENMOD can be used for multiple Poisson/negative binomial modelling.

10. ANNEXES

10.1. Business rules for standard data derivations and statistical methods

This section contains GSK Vaccines' standard rules for data display and derivation for clinical and epidemiological studies. These rules will be applied along with those detailed in section 9 (additional study-specific rules).

10.1.1. Age

Age of infant will be expressed in months and will be computed as the number of complete calendar months between the date of birth (DOB) and the date of event. For example:

DOB = 10JUN2017, Date of event = 09JUL2018 -> Age = 12 months

DOB = 10JUN2017, Date of event = 10JUL2018 -> Age = 13 months

Age of the mother at the time of childbirth will be expressed in years and will be computed as the number of complete calendar years between the birth date of the infant and the birth date of the mother. For example:

DOB = 10SEP1983, Date of V1 = 09SEP2018 -> Age = 34 years

DOB = 10SEP1983, Date of V1 = 10SEP2018 -> Age = 35 years

10.1.2. Handling of missing data

10.1.2.1. Dates

When partially completed dates (i.e. with missing day or month) are used in calculations, the following standard rules will be applied:

- A missing day will be replaced by 15
- A missing day and month will be replaced by June 30th.

10.1.2.2. Laboratory data

Missing laboratory results (including immunological data) will not be replaced.

10.1.2.2.1. Studies with paper diaries

For studies using paper diaries which have questions in the CRF indicating the presence or absence of solicited symptoms, the following rules are applicable.

Denominators for the summary of local (or general) solicited symptoms will be calculated using the number of subjects who respond “Yes” or “No” to the question concerning the occurrence of local (or general) symptoms.

When a specific symptom is marked as having not occurred following a specific vaccination (i.e. SDTM CE.CEOCCUR=N for the specified post-vaccination period for the symptom in question), all daily measurements will be imputed as Grade 0.

When a specific symptom is marked as having occurred following a specific vaccination (i.e. SDTM CE.CEOCCUR=Y for the specified post-vaccination period for the symptom in question), any missing daily recordings will be given imputed values to allow them to contribute to the ‘Any’ rows but not to specific grade rows of the symptom summary tables.

When the occurrence of a specific symptom is not present (i.e. SDTM CE.CEOCCUR is neither Y nor N for the specified post-vaccination period for the symptom in question) but the group of symptoms (local or general) is marked as having occurred (i.e. SDTM CE.CEOCCUR=Y), all missing daily recordings will be given imputed values to allow them to contribute to the ‘Any’ rows but not to specific grade rows of the symptom summary tables.

The following table shows how subjects contribute to each category for a specific solicited symptom over the Day X to Day Y post-vaccination period:

Solicited symptom category	Subjects included in the calculation of the numerator
Any	All subjects with at least one occurrence of the symptom at grade 1, grade 2, or grade 3 between Day X and Day Y or with the symptom marked as present and at least one missing daily recording between Day X and Day Y
At least grade 1	All subjects with at least one occurrence of the symptom at grade 1, grade 2, or grade 3 between Day X and Day Y
At least grade 2	All subjects with at least one occurrence of the symptom at grade 2 or grade 3 between Day X and Day Y
At least grade 3	All subjects with at least one occurrence of the symptom at grade 3 between Day X and Day Y

